5.1 Assignment of analysis sets

Final decisions regarding the assignment of subjects to analysis sets will be made during the review of study data and documented in the final list of important deviations, validity findings and assignment to analysis set(s) (see section 4.6).

The statistical analysis sets are defined as follows:

SAFety analysis set (SAF)

All subjects with at least one intake of study drug.

Subjects who were assigned to treatment but did not receive study medication will not be included in the SAF. As the number of these excluded subjects is anticipated to be negligible, if at all any exist in this design, an "all assigned treatment analysis set" will not be generated.

(modified) Intent To Treat Set (ITT)

All subjects of the SAF, who have infusion/bleeding data.

Per Protocol Set (PPS)

All ITT subjects who completed Part A and Part B of the study with no major protocol deviations.

Major protocol violations would be for example:

- Severe hemophilia A not confirmed
- Evidence of inhibitor antibody present at the time of screening.
- MTP has previously received more than 3 exposure days with any FVIII product, PUP has received any amount of FVIII
- In the prophylactic period here was/were at least
 - \circ one instance of >30 days between infusions
 - \circ two instances of >21 days between infusions
 - \circ three instances of >14 days between infusions

PharmacoKinetic Analysis Set (PK)

Statistical Analysis Plan PH-41074 Protocol No.: BAY 81-8973 / 13400

Page: 12 of 19:

Not applicable to this interim analysis, as it is not expected to get enough subjects for a reasonable analysis from part B. There will be an analysis of the pharmacokinetic data for the final CSR.

Listing Only Set (LOS)

Subjects who do not belong to SAF will not be included into statistical considerations. These subjects are classified as 'listing only set' (LOS). Number of screening failures and dropouts will be tabulated.

6. Statistical Methodology

The efficacy analyses will be based on the ITT and sensitivity analyses will be based on the PPS as appropriate.

The primary analysis population for the safety analysis will be the SAF.

6.1 **Population characteristics**

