5.1 Eligibility

5.1.1 Inclusion criteria

In order to be included in the study, subjects must *have (as of Amd 1)* all of the following criteria upon evaluation at the Screening or Baseline visit:

Part A (as of Amd 1)

1. Male, age ≤ 12 years. ***Enrollment will begin with subjects 6-12 years before it is opened to all age groups. (as of Amd 1, Amd 3)***
2. Severe hemophilia A defined as $< 1\%$ FVIII concentration (FVIII:C) based on ***documented prior testing (as of Amd 1) or screening laboratory (Amd 3)***
3. ≥ 50 ED with any FVIII ***concentrate (as of Amd 1, Amd 3)***
4. No current evidence of inhibitor antibody measured using the Nijmegen-modified Bethesda assay [< 0.6 Bethesda units (BU)/mL] within 2-3 weeks ***of last FVIII (as of Amd 1) administration. PTPs (as of Amd 1) may not receive FVIII within 48 h prior to the collection of samples for inhibitor testing at the Screening visit. (as of Amd 1)***
5. No history of FVIII inhibitor formation. Documentation of negative result in medical records required. [Subjects with a maximum historical titer of 1.0 BU on no more than 1 occasion with the classical Bethesda assay but at least 3 successive negative (< 0.6 BU) results thereafter are eligible.]
6. Willingness and ability of subjects and/or parents to complete training in the use of the electronic patient diary (EPD) and to document ***infusions (as of Amd 1)*** during the study.
7. Written informed consent by parent/legal representative. Assent should be sought from subjects if appropriate

- **Part B (PUPs/MTPs):** *Enrollment s may start after safety is evaluated in 20 children in Part A with 50 ED (as of Amds 1 and 6).*

1. Male, <6 years (as of Amd 3)

2. Severe hemophilia A defined as < 1% FVIII:C based on *prior documented testing or confirmed on (as of Amd 1, Amd 3) screening* laboratory

3a. **PUPs:** No previous exposure to any FVIII *product (as of Amd 1)*

3b. **MTPs:** *Have no more than 3 EDs with any FVIII product and who have no current evidence of inhibitor antibody measured centrally using the Nijmegen-modified Bethesda assay [<0.2 Bethesda units (BU)/mL] at screening, with confirmation using local laboratory testing at baseline (<0.6 Bethesda unit [BU/mL]) (as of Amd 7). MTPs may not receive FVIII within 48 h prior to the collection of samples for inhibitor testing at the Screening and Baseline visits. (as of Amd 6 and Amd 7)*

3c. **MTPs:** *No history of FVIII inhibitor formation. (as of Amd 6)*

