5.1.2 Exclusion criteria

Subjects who meet any of the following criteria at Screening or Baseline visits will be excluded from participating in the study:

Parts A and B

1. Any individual with another bleeding *disorder (as of Amd 1)* that is different from Hemophilia A (eg, von Willebrand disease, Hemophilia B)
2. Any individual with thrombocytopenia (platelet count $< 100\ 000/\text{mm}^3$)
3. *Creatinine $> 2x$ upper limit of normal or Aspartate aminotransferase (AST)/Alanine aminotransferase (ALT) $> 5x$ upper limit of normal (as of Amd 1)*
4. Any individual without *a* negative inhibitor testing *at screening* (except for PUPs) (as of Amd 3)
5. Any individual who is receiving *chemotherapy, immune modulatory drugs (Intravenous immunoglobulin [IVIG], cyclosporine, chronic use of oral or i.v. corticosteroids), has received another investigational FVIII product* within the last month, or received another experimental drug within *the last 3 months. (as of Amd 1, Amd 3)*
6. Any individual who requires any pre-medication to tolerate FVIII *treatment (as of Amd 1)* (eg, antihistamines)

7. Any individual who is unwilling to comply with study visits or other protocol requirements, for example (eg. prophylaxis treatment) or is not suitable for participation in this study for any reason, according to the Investigator's **judgment. (as of Amd 1)**
8. Known hypersensitivity to active substance, mouse, or hamster protein.
9. Previous participation in this study

Part B only (*PUPs/MTPs [as of Amd 6]*):

10. First treatment with BAY 81-8973 **for high risk bleeding situations (eg, surgery, intracranial bleed), or requiring intensive or prolonged treatment. (as of Amd 1)**
11. **Unable to tolerate volume of blood draws required for study participation (See Section 14.4). (as of Amd 1)**

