8.2 Analysis sets

Efficacy and safety data will be collected from all subjects who received study medication. The intent-to-treat (ITT) population will include all subjects randomized into the study who received study drug. The per-protocol population will exclude subjects who are deemed invalid in the Validity Review Report. Subjects from Part A and Part B will be summarized separately. (as of Amd 1)

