5.1 Assignment of analysis sets

The safety analysis set (SAF) will include all subjects who were entered into the study and received study drug. The intent-to-treat analysis set (ITT) will include all subjects in the SAF who have infusion/bleeding data from the EPD. The per-protocol analysis set (PPS) will include all ITT subjects who have no major protocol deviations and have EPD data. The ITT will be used for the primary efficacy analysis. The efficacy analysis of the PPS will be considered supportive. Data from Part B and the extensions will be summarized separately.

Specific rules for major protocol deviations will be documented in the "Protocol Deviations Document" (PDD) prior to validity review meeting. Final decisions regarding the assignment of subjects to analysis sets will be made during the Validity Review Meeting and documented in the Validity Review Report.

Subjects will be excluded from the PPS for non-compliance if they violate any of the following criteria (for PTPs only):

- at least 1 interval between all infusions > 30 days
- at least 2 intervals between all infusions > 21 days
- at least 3 intervals between all infusions > 14 days
- number of infusions < 80% number of expected infusions [use expected number of infusions = (prescribed number of infusions per week) * (last datetime in study 1st datetime in study) / (60*24*7)]
- at least 20% of prophylaxis infusions at a dose level < 15 IU/kg (for PTPs)
- at least 20% of prophylaxis infusions at a dose level < 10 IU/kg (for PUPs) [Note: not applicable to this SAP)

All tables will summarize data with columns for PTP 0-<6 years, PTP 6-12 years, and Total.

Pharmacokinetic Analysis Set

All subjects with evaluable PK-data will be included in the analysis of pharmacokinetic data.

Subgroups:

Subgroup tables will be provided. Possible subgroups for number of bleeds within 48 hours after prophylaxis per year and number of bleeds per year to be presented are:

- Prophylaxis Treatment regimen (<=2x/week, >2x/week)
- Average prophylaxis dose high (>=30 IU/kg), low dose (<30 IU/kg)
- Average prophylaxis dose/week high (>=80 IU/kg), low (<80 IU/kg)
- prior treatment (on-demand, prophylaxis)
- Race Group (white, non-white)
- Region (North America, Europe, Israel)
- Number of Bleeds during previous 12 months (<median, >=median)
- Number of Joint Bleeds during previous 12 months (<median, >=median)
- Presence of Target Joint (no, yes)

6. Statistical Methodology

6.1 **Population characteristics**

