4.2 Handling of Dropouts

In this study, all efforts must be taken to engage patients to comply with all study procedures and to continue to be followed until the end of the study.

A subject who discontinues study participation prematurely for any reason is defined as a "dropout" if the subject has received at least one dose of study drug. At the time of discontinuation, subjects should be requested to have a final visit to have performed the procedures and evaluations scheduled for the final study visit as described for last visit. Subjects who are withdrawn after the start of treatment will not be replaced.

A subject is regarded a "screening failure" if he terminates the study for any reason (e.g., failure to satisfy the selection criteria) prior to the time point used for the definition of "dropout".

In all cases, the reason for withdrawal must be recorded in the electronic case report form (eCRF) and in the subject's medical records.

The number of subjects who prematurely discontinue the study during the treatment phase or during the post-treatment observation phase for any reason, as well as the reasons for premature discontinuation of study, will be displayed.

Subjects who prematurely withdraw prophylaxis treatment due to inhibitor development will be considered premature discontinuations from Part B, even though they may continue with ITI treatment in the extension phase. For this reason a separate tabulation of the reason for premature termination will be given, where all reasons connected to ITI or inhibitors will be combined to "INHIBITOR MANAGEMENT". In addition subjects, who prematurely

discontinued part B without a clinical reason (inhibitor, AE) or withdrawal of informed consent or protocol violation, but just for logistical problems to match exactly the 50 EDs, will be counted as completers in this table.

Subjects can be withdrawn at their parent's request, or at the investigator's discretion due to, for example, development of inhibitory antibody or lack of compliance. The reasons for withdrawal will be listed. The annualized number of total bleeds will be calculated for these withdrawn subjects, and the time of the last procedure in a visit or the last infusion in the EPD will serve as the end time point used for calculation.

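### The Part B per-protocol set requires completing both Part A and Part B, which no child can do; read as completing the part entered, it drops children withdrawn for an inhibitor

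*SAP*

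**What the plan says.** The Part B SAP (version 2.0, 22 Jan 2020), section 5.1, defines the PPS as "All ITT subjects who completed Part A and Part B of the study with no major protocol deviations". Its examples of major deviations include an inhibitor present at screening, too much prior FVIII exposure and long gaps between infusions. An inhibitor arising on treatment is not among them. Final assignment to analysis sets is left to the review of study data. Section 6 bases efficacy on the ITT and sensitivity analyses on the PPS where appropriate.

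The trial's other two definitions contain no completion condition. Protocol section 8.2: "The per-protocol population will exclude subjects who are deemed invalid in the Validity Review Report". Part A SAP, section 5.1: "The per-protocol analysis set (PPS) will include all ITT subjects who have no major protocol deviations and have EPD data".

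Neither the change log in section 7 of the Part B SAP nor the supplement of 28 Jan 2020 touches the PPS sentence.

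**The concern.** Two things are wrong. First, the rule cannot be applied as written, because Parts A and B recruit populations that do not overlap. Someone must reinterpret it when set membership is decided. The trial is open-label, so bleeding and inhibitor results can be known by then.

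Second, the obvious repair leaves a worse problem. If the sentence means that the child completed the part he entered, children who leave Part B because of an inhibitor fall out of the set, while low-titer children who stay to the final visit remain. Membership then depends on the course of an inhibitor, which the SAP's own background section treats as the most important complication of treatment. A sensitivity set filtered in this way cannot show that the ITT bleed rates are robust, because it removes a group whose results could differ.

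**Working it through.** The plan states no PPS size, so there is no figure to reproduce. The check sets the definition against the entry and completion rules and then does simple arithmetic for scale.

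**1. Can any child complete both parts?** (Protocol 5.1.1 and 5.1.2)

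- Part A, inclusion 3: "≥ 50 ED with any FVIII" concentrate.
- Part B, inclusion 3a: PUPs have 0 prior ED. Inclusion 3b, MTPs: "Have no more than 3 EDs with any FVIII product".
- Exclusion 9, both parts: "Previous participation in this study".

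The prior-exposure ranges are {50, 51, ...} and {0, 1, 2, 3}, and they have no value in common. A Part B child who later accumulates 50 ED cannot cross to Part A because exclusion 9 bars him. A Part A child can never return to 3 ED or fewer. Section 1 of the Part B SAP also says the Part A analysis is complete and reported. Result: 0 eligible children.

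**2. What does the reading 'completed the part entered' do?** (Part B SAP, sections 1, 4.2 and 6.2.2)

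- Section 1 says children who develop an inhibitor are to leave Part B, for the extension or for treatment outside the study.
- Section 4.2: "Subjects who prematurely withdraw prophylaxis treatment due to inhibitor development will be considered premature discontinuations from Part B".
- Section 4.2 relaxes the idea of a completer once, for children who stop "just for logistical problems to match exactly the 50 EDs, will be counted as completers in this table". That rule is limited to one disposition table and expressly leaves out children who stop for an inhibitor. 'Completed' is not defined for the PPS.
- Section 6.2.2 lets the low-titer period run to the final visit, so such a child can still complete Part B.

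Since an on-treatment inhibitor is not a listed deviation, the completion condition itself is what removes the withdrawn children.

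**3. How many could that be?** Part B plans at least 25 PUPs plus about 25 more PUPs/MTPs: 25 + 25 = 50.

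Dropped = N × inhibitor rate × fraction of those children withdrawn. Left = N − dropped.

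For N = 50:

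| Assumed inhibitor rate | All withdrawn: dropped / left | Half withdrawn: dropped / left |
|---|---|---|
| 20% | 10 / 40 | 5 / 45 |
| 30% | 15 / 35 | 7.5 / 42.5 |
| 40% | 20 / 30 | 10 / 40 |
| 50% | 25 / 25 | 12.5 / 37.5 |

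For the minimum N = 25 every entry halves: 2.5 to 12.5 dropped, 22.5 to 12.5 left.

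The rates and fractions are assumptions. The only anchor in the documents is the SAP background statement that inhibitors occur in up to half of patients with severe disease. That is an incidence ceiling, not a withdrawal rate.

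**The case against.** The strongest reply is that this is a drafting slip in a set on which little depends. The phrase looks like study-level wording carried into a Part B document, and any reader would take it to mean the part the child entered. Section 6.2 names no PPS table, the efficacy analysis is exploratory (appendix 9.1), and efficacy is already displayed by inhibitor status, so readers can see what removing these children does. Reasons for exclusion are to be tabulated (section 6.1.1), and assignments are to be documented (section 4.6). The dataset specifications, which are part of the SAP but not available here, might define the flag properly. A completion condition in a per-protocol set is also a legitimate choice, and deleting it readmits children who left early for unrelated reasons.

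Most of this limits the impact without repairing the rule. The distributive reading is indeed the natural one, but it is the reading that selects on the outcome. Tabulating exclusions makes the problem visible and does not remove it. The unseen specifications cannot be relied on either way. A completion condition can be defended in principle, but here it departs without explanation from the protocol and the Part A SAP. The point that the headcounts are assumed, and say nothing about the direction or size of any shift in bleed rate, stands.

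**Conclusion.** The concern holds. As written, the Part B PPS contains 0 of about 50 children; this follows from the entry criteria and needs no assumption. Under the workable reading it loses every child withdrawn for an inhibitor. That is 5 to 25 of 50 before any other exclusion, if 20% to 50% develop an inhibitor and half or all of them are withdrawn. No effect on the annualized bleed rate can be derived from the documents.

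The consequence is limited to the PPS sensitivity analyses. ITT efficacy, safety and inhibitor incidence, and the displays by inhibitor status stand as planned. It should be fixed because an operative set definition is unusable as it stands, and its likely repair would be made at data review without a pre-specified rule.

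**What to change.** In section 5.1 of the Part B SAP, delete the completion condition and define the set along these lines:

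> All Part B ITT subjects with no major protocol deviations. Inhibitor development and resulting withdrawal are outcomes and are not reasons for exclusion from the PPS. Each child's data count to the end of his Part B participation.

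No cut-off should be set at inhibitor confirmation, so that bleeds after a low-titer inhibitor stay in. The end point fits the rule section 4.2 already gives for withdrawn children, whose bleed rate runs to the last visit procedure or the last infusion in the diary. The change also removes the completion condition that sets this PPS apart from Protocol 8.2 and the Part A SAP.

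Cost: one clause deleted and two sentences added, with no new data or subjects.

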6.1.1 Demography and baseline characteristics

Demographic and baseline data will be evaluated descriptively for the SAF resp. for the ITT. Data will be described by pre-treatment (PUPs/MTPs) and where meaningful with the inhibitor status as given in 4.1. No statistical tests will be performed to compare these characteristics across different groups.

Descriptive statistics (such as mean, standard deviation, median, minimum and maximum) will be provided for continuous variables such as

- age at Screening,
- body weight,
- body height,
- BMI.

Counts and (appropriate) percentages will be provided for categorical variables such as

- sex,
- race/ethnicity.

Reasons for exclusion from analysis populations will be summarized.

6.1.2 Medical history

Medical history data will be evaluated by frequency tables, showing the number and percentage of subjects with medical history findings (i.e., previous diagnoses, diseases or surgeries) that started before signing of the informed consent and that are considered relevant for the subject's study eligibility using MedDRA Primary System Organ Class / Preferred Term.

Statistical Analysis Plan PH-41074 Protocol No.: BAY 81-8973 / 13400

3 / 13400

Page: 13 of 19:

6.1.3 Disease history

The following baseline characteristics of the disease history will be evaluated descriptively for the ITT, by pre-treatment (PUPs/MTPs) and overall:

- Age of hemophilia diagnosis
- Start of therapy (MTPs)
- Family history of hemophilia
- FVIII level and type of assay
- Family and personal history of past inhibitor formation
- Number and type of bleeds in the past 12 months
- Presence and location of target joints

6.1.4 Medication history

Medication history data including include prior FVIII products (MTPs) as well as a history of other prior and current medications will be evaluated descriptively for the SAF, both overall and by pre-treatment (PUPs/MTPs).

6.2 Efficacy

All subjects receiving study drug who have infusion/bleeding data from the EPD will be included in the efficacy analysis.

Primary Efficacy Analysis

The primary efficacy variable according to protocol will be the annualized number of total bleeds (sum of spontaneous bleeds, trauma bleeds, untreated bleeds, and 'other' bleeds) that occur within 48 hours after all prophylaxis infusions. 'Other' bleeds are infusions with reason given as 'other'.

For this primary efficacy variable, the number of data available and missing data, mean, standard deviation (SD), minimum (Min), quartiles, median, and maximum (Max) will be summarized and presented.

Additional Efficacy Analysis

Also summarized will be annualized number of joint bleeds, spontaneous bleeds, and trauma bleeds that occur within 48 hours after all prophylaxis infusions. Additional variables summarized will be annualized number of total bleeds, joint bleeds, spontaneous bleeds, and trauma bleeds as well as the annualized numbers.

Other variables summarized will be the number of treatments required to control all bleeds and the subject's assessment of the response to treatment of all bleeds (excellent, good, moderate, or poor), further on description of joint bleeds according to site as well as proportion of subjects with no bleed

FVIII usage/consumption will be described expressed as number of infusions, number of prophylaxis infusions, and number of infusions to treat breakthrough bleeds. Infusions will be summarized in IU, IU/kg, IU/kg/year, IU/kg/infusion, IU/year, and IU/infusion.

All efficacy variables will be summarized using the ITT analysis set. The summary of bleeds, the exposure to study drug and the treatment administration for bleeds will also be given in the ITT.

The number of infusions used to treat a bleed will be summarized. The number of infusions used to treat a bleed is defined as the first infusion to treat the bleed plus all follow-up infusions to treat the same bleed, if any. The proportion of bleeds controlled by ≤ 2 and ≥ 2 infusions will be presented.

